## 8.1 Primary Analysis of Prevention Efficacy

The time between enrollment and the date of HIV-1 infection diagnosis determined according to Section 5.3 is evaluated in the MITT cohort. The failure times of participants never observed to be diagnosed with HIV-1 infection are right-censored at the date of the last HIV-negative test or the Week 80 visit, whichever occurs earlier.

Let PE denote the overall prevention efficacy by the Week 80 visit of the 10 mg/kg and 30 mg/kg mAb groups pooled together compared to the control group. We define the primary PE parameter as

$$PE = \{1 - \text{cumulative incidence ratio (pooled mAb groups/control group)} \\ \text{of the primary efficacy endpoint by the Week 80 visit}\} \times 100\%, \quad (1)$$

where the cumulative incidence ratio is the probability of the primary efficacy endpoint by the Week 80 visit for participants assigned to receive the mAb divided by the probability of the primary efficacy endpoint by the Week 80 visit for participants assigned to receive control. More specifically, the primary PE parameter,  $PE(t)$ , will be estimated at a fixed time point  $t$  chosen to be the latest possible time point when stable estimation using follow-up data through the Week 80 visit can be achieved; this is operationalized by defining  $t$  as the maximum time point with 150 participants at risk for the primary endpoint in each of the placebo and individual VRC01 groups. All times-to-event will be right-censored at the Week 80 visit or earlier following the operational rules summarized in Table 1. Note that the fixed time point  $t$  will likely differ for the two AMP trials given the dynamic visit windows. By definition of the stratified estimator, the trial-pooled analysis will use the smaller of the two fixed time points  $t$ . Additionally, note that, due to differences between Schedules 1 and 4, the operational rules in Table 1 imply that an infection endpoint observed in Schedule 4 after the hypothetical Schedule 4 Week 80 visit would be excluded from primary endpoints,

Table 1: Operational rules for right-censoring of times-to-event at the Week 80 visit

HIV status	Visit attendance scenario		Censoring rule	
HIV-Uninfected	Attended s1 wk 80 visit		Censor at s1 wk 80 sample draw date	
	Missed s1 wk 80 visit	Attended s1 post-wk 80 visit	Censor at target s1 wk 80 visit date	
		Attended s4 post-wk 80 visit	Censor at maximum of (hypothetical s4 wk 80 visit  , last s1 sample draw date)	
		Did not attend post-week 80 visit in s1 or s4	Censor at last HIV-uninfected sample draw date	
HIV-Infected	Infected in s1 on or before s1 wk 80 visit		Infected, use adjudicated diagnosis date	
	Infected in s1 after s1 wk 80 visit	Attended s1 wk 80 visit		Censor at s1 wk 80 sample draw date
		Missed s1 wk 80 visit	Evidence of HIV-negative status at post-s1 wk 80 visit	Censor at target s1 wk 80 visit date
			No evidence of HIV-negative status at post-s1 wk 80 visit	Censor at last HIV-uninfected sample draw date
	Entered s4 at or before hypothetical s4 wk 80 visit 	Infected on or before hypothetical s4 wk 80 visit		Infected, use adjudicated diagnosis date
		Infected after hypothetical s4 wk 80 visit	Evidence of HIV-negative status at post-hypothetical s4 wk 80 visit	Censor at hypothetical s4 wk 80 visit  date
			No evidence of HIV-negative status at post-hypothetical s4 wk 80 visit	Censor at last HIV-uninfected sample draw date
	Entered s4 after the hypothetical s4 wk 80 visit and diagnosed after the first s4 visit		Censor at maximum of (hypothetical s4 wk 80 visit, last s1 HIV-uninfected sample draw date)	
Entered s4 after the hypothetical s4 wk 80 visit and diagnosed immediately		Censor at last s1 HIV-uninfected sample draw date 		

- Abbreviations: wk = visit label for target visit week as defined in the study protocol (Appendix J for Schedule 1 and Appendix M for Schedule 4), s1 = Schedule 1, s4 = Schedule 4.
- Actual visit dates may differ from the implied week in the target visit label due to (1) dynamic visit scheduling in schedule 1, and (2) visit windows in schedules 1 and 4.
- All censoring times are based on sample draw dates or target visit dates (where appropriate). Visit windows are not used because (1) Schedule 1 and Schedule 4 visit windows are quite different (s1 allowable wk 80 visit window is +/- 7 days, s4 allowable windows are -41/+42 days), and (2) since a hypothetical wk 80 visit is constructed in s4, unnecessarily complicated to construct a hypothetical s4 wk 80 visit window, which would overlap with other s4 visit windows if the same pattern were followed and would be an entirely unique visit window if no overlap were ensured.
- Hypothetical s4 week 80 visit is defined as exactly 560 days post-enrollment. Justification: unlike s1, s4 visits are all relative to enrollment and occur independently of each other, so it's preferable to define a hypothetical wk 80 visit as 560 days post-enrollment than to use a midpoint estimator and/or some other dynamic method which doesn't correspond to s4's structure.
- If a participant enters s4 at wk 88 or wk 104 and is immediately diagnosed, cannot determine whether infection occurred in s1 (clearly before the target s1 wk 80 visit) or in s4 (clearly after the hypothetical s4 wk 80 visit).

while an infection endpoint observed in Schedule 1 at the same time post-enrollment would be included as a primary endpoint if the endpoint was registered before or at the Schedule 1 Week 80 visit.

Each of the two cumulative incidence parameters in (1) will be estimated using the transformed Nelson-Aalen estimator for the cumulative hazard function evaluated at time  $t$  defined in the preceding paragraph. We will use the delta method to obtain the asymptotic 95% CI for the log cumulative incidence ratio (pooled mAb/control) and then back-transform these confidence bounds to the PE scale. Both the point estimate and the 95% CI for PE will be reported. If there are more than 10 HIV-1 primary endpoints in each of the VRC01 dose groups, then the Nelson-Aalen estimator for the cumulative hazard function will be computed separately for each dose group and the weighted average of the dose group-specific estimates, with the weight 0.5 assigned to each dose group, will be transformed for inference about PE. The variance estimate of the overall averaged cumulative hazard estimator will

be used to obtain the variance estimate on the log cumulative incidence ratio scale for calculating confidence intervals. For trial-pooled analyses, if there are more than 10 primary endpoints in each stratum defined by trial and treatment group, the Nelson-Aalen estimator will be computed separately in each of the 6 strata (4 VRC01 dose group strata and 2 control group strata), and separate weighted averages of the VRC01 dose-group and control-group stratum-specific estimates, with weights 0.25 assigned to each VRC01 dose-group stratum and weights 0.5 assigned to each control-group stratum, will be transformed for inference about the trial-pooled PE.

PE is the target parameter for the primary analysis of overall PE. The primary analysis tests the null hypothesis

$$H_0 : PE = 0\% \text{ versus the alternative hypothesis } H_1 : PE \neq 0\% \quad (2)$$

using a 2-sided  $\alpha = 0.05$  level Wald test of the equality of log cumulative hazard functions at 80 weeks for the pooled mAb group and the control group. Note that the critical value for determining whether the effect of VRC01 on prevention of HIV-1 acquisition is significant at the two-sided 0.05 level will not require adjustment for the interim monitoring of PE for potential harm, non-efficacy, and high efficacy described in Section 9.2. This is because this monitoring is designed to have minimal impact on the type-I error/power of the study. Moreover, whereas interim monitoring for positive PE would mean that the actual type-I error of the study is inflated above the nominal level, interim monitoring for potential harm, non-efficacy, and high efficacy has the effect of decreasing the actual type-I error rate below the nominal level. In other words, use of the unadjusted critical value leads to conservative (as opposed to anti-conservative) inference, and our simulations show that the degree of conservatism is minimal.

The timing of infections will be described separately for the pooled mAb group and the control group by the respective cumulative incidence curves of the time between first infusion and the date of HIV-1 infection diagnosis. Each curve will be estimated by a transformed Nelson-Aalen estimator for the cumulative hazard function. To obtain a pointwise 95% CI, we will use the delta method to obtain the asymptotic 95% CI for the log cumulative incidence over time and then exponentiate the confidence bounds. As for PE, if there are more than 10 HIV infection events in each of the VRC01 dose groups, then the above estimators will be computed separately for each dose group and aggregated for inference on the pooled mAb group cumulative incidence.

Additionally, cumulative PE over time will be reported. To obtain pointwise 95% CIs, first we will use the delta method to obtain asymptotic 95% CIs for the log cumulative incidence ratio (pooled VRC01/control) over time and then back-transform the confidence bounds to the PE scale. The simultaneous 95% confidence interval for cumulative PE over time will be obtained following the method of Parzen, Wei, and Ying (1997). The same method will be applied to obtain an estimate of cumulative PE on the additive difference-scale (control group minus pooled VRC01 group) with pointwise and simultaneous 95% confidence intervals. This analysis is informative because it communicates about benefits and risk on an absolute scale:

for example under the assumption that assignment to a VRC01 arm does not increase the risk of infection for any participant, the estimate at a given time  $t$  is interpreted as the probability a participant assigned to a VRC01 arm has their infection averted compared to, counter to fact, had they been assigned to placebo.

## 8.2 Secondary Analyses of Prevention Efficacy

Secondary analyses assess PE parameters for the mAb dose groups separately. Let PE10 be the overall prevention efficacy of the 10 mg/kg mAb group and let PE30 be the overall prevention efficacy of the 30 mg/kg mAb group, defined as

$$PE10 = \left\{ 1 - \text{cumulative incidence ratio (mAb 10 mg/kg group/control group)} \right. \\ \left. \text{of the primary efficacy endpoint by 80 weeks} \right\} \times 100\%,$$

and

$$PE30 = \left\{ 1 - \text{cumulative incidence ratio (mAb 30 mg/kg group/control group)} \right. \\ \left. \text{of the primary efficacy endpoint by 80 weeks} \right\} \times 100\%.$$

The PE10 and PE30 parameters will be assessed using the same estimation method as described in Section 8.1.

We will conduct secondary analyses to test the null hypotheses

$$H_0 : PE10 = 0\% \text{ versus the alternative hypothesis } H_1 : PE10 \neq 0\%$$

and

$$H_0 : PE30 = 0\% \text{ versus the alternative hypothesis } H_1 : PE30 \neq 0\%$$

using 2-sided  $\alpha = 0.05$  level Wald tests described in Section 8.1. Both unadjusted p-values and Holm–Bonferroni-adjusted p-values (Holm, 1979) will be reported for each of the individual dose versus control group analyses.

In addition, the following secondary analyses of PE will be conducted:

- (i) Assess a dose-response effect by testing the null hypothesis

$$H_0 : \text{cumulative HIV-1 incidence by 80 weeks is equal in the three study groups versus} \\ H_1 : 0\% \leq PE10 \leq PE30 \text{ with at least one strict inequality.}$$

- (ii) Test the null hypothesis that the cumulative HIV-1 incidence by 80 weeks is equal in the three study groups versus the alternative hypothesis that there are some differences.

- (iii) Test the null hypothesis that the cumulative HIV-1 incidence by 80 weeks is equal in the two mAb groups versus the alternative hypothesis that PE30 is greater than PE10, which would demonstrate that assignment to a higher mAb dose level causes higher PE.

Hypotheses (i)–(iii) will be tested using cumulative hazard function based Wald tests. Define the Wald test statistic

$$W_{i,j} = \frac{\log \widehat{\Lambda}_i(80 \text{ weeks}) - \log \widehat{\Lambda}_j(80 \text{ weeks})}{\sqrt{\widehat{\text{var}}\{\log \widehat{\Lambda}_i(80 \text{ weeks})\} + \widehat{\text{var}}\{\log \widehat{\Lambda}_j(80 \text{ weeks})\}}},$$

where  $\widehat{\Lambda}(\cdot)$  is the Nelson-Aalen estimator and  $i, j \in \{c, 10, 30\}$ ,  $i \neq j$ , represent the control, 10 mg/kg mAb, and 30 mg/kg mAb group, respectively. The test statistic considers the estimated variance of the Nelson-Aalen estimator proposed in Aalen (1978).

The alternative hypothesis in (i) is equivalent to  $\widetilde{H}_1 : \Lambda_c(t_0) \geq \Lambda_{10}(t_0) \geq \Lambda_{30}(t_0)$ ,  $t_0 = 80$  weeks, with at least one strict inequality, and therefore the test of (i) will reject  $H_0$  if both  $W_{c,10} \geq \Phi^{-1}(0.975)$  and  $W_{10,30} \geq \Phi^{-1}(0.975)$ , where  $\Phi^{-1}$  is the quantile function of the standard normal distribution. The test of (ii) will reject  $H_0$  if at least one of  $|W_{c,10}| \geq \Phi^{-1}(0.975)$  and  $|W_{10,30}| \geq \Phi^{-1}(0.975)$  holds. The test of (iii) will reject  $H_0$  if  $W_{10,30} \geq \Phi^{-1}(0.975)$ .

As a supportive analysis of the hypotheses in (2), targeted minimum loss-based estimation (TMLE) may be used to estimate cumulative incidences of the primary efficacy endpoint over time for the pooled mAb arm and the control arm. Iterative mean-based TMLE is used for this analysis as described in Benkeser, Carone, and Gilbert (2016). The Super Learner (van der Laan, Polley, and Hubbard, 2007) is used to generate initial estimates of the conditional censoring distribution and the iterated conditional means. The Super Learner library includes both parametric and nonparametric algorithms: generalized linear models, generalized additive models with 2 or 3 degrees of freedom, a regression tree (Breiman et al., 1984), and a random forest (Breiman, 2001) (specified in Table 2). Each method considers adjustment for baseline demographic covariates, the baseline behavioral risk score built via supervised learning as described in Section 8.6, and two-way interactions of these terms. The baseline demographics to adjust for are country (if there are at least 10 total primary HIV-1 infection endpoints in a country – otherwise categories are collapsed) and AMP study (for analyses that pool the two AMP trials). The candidate algorithms in the Super Learner library consider various adjustments for time, as shown in Table 2. TMLE analyses will produce plots of estimated cumulative PE on both the multiplicative mAb efficacy and additive-difference scales, as done for the primary analyses. The TMLE analyses will be implemented using the *survtmle* R package available at CRAN.

PE parameters will be estimated by 1 minus the ratio (pooled mAb groups/control group) of these tMLE estimators. Influence-curve based variance estimators of each cumulative incidence is used, and the delta method applied to obtain the variance estimator of the log

Table 2: Models included in the Super Learner library.  $Z$  denotes a mAb group assignment,  $B$  baseline behavioral risk score as described in Section 8.6, and  $W$  a vector of baseline demographic covariates. The columns indicate what type of model was used (glm = generalized linear model, step = stepwise glm using both AIC and BIC as selection criteria, and gam = generalized additive model), how time was modeled ( $\emptyset$  denotes time was omitted from the model, **factor(t)** indicates dummy variables were used), and what covariates were included ( $x * y$  indicates a cross product between covariates  $x$  and  $y$ ). We use  $s(x; df = d)$  to denote that variable  $x$  was modeled using a polynomial spline of degree  $d$ .

Model type	Time	Covariates
Conditional mean estimates		
glm	$\emptyset$	$Z$
glm	$\emptyset$	$Z + B + W$
glm	$\emptyset$	$Z * B$
step	$\emptyset$	$Z * B + W$
Censoring estimates		
glm	factor(t)	$\emptyset$
glm	factor(t)	$Z * t$
glm	$\emptyset$	$Z$
glm	$\emptyset$	$Z + B + W$
glm	$t$	$Z$
glm	$t$	$Z + B + W$
glm	$\log(t)$	$Z$
glm	$\log(t)$	$Z + B + W$
step	factor(t)	$Z + B + W$
step	$t$	$Z + B + W$
step	$\log(t)$	$Z + B + W$
gam	$s(t, 3)$	$Z$
gam	$s(t, 3)$	$Z + B + W$
gam	$s(t, 2)$	$Z$
gam	$s(t, 2)$	$Z + B + W$

cumulative incidence ratio. Point estimates and 95% pointwise and simultaneous Wald CIs for cumulative incidence curves and  $PE(t)$  curves will be plotted. For the final timepoint of 80 weeks, 2-sided Wald p-values will be reported.

In addition to studying PE based on cumulative incidences of the primary efficacy endpoint over time, secondary analyses will assess hazard ratio based PE defined as

$$PE = \{1 - \text{hazard ratio (pooled mAb groups/control group)} \\ \text{of the primary efficacy endpoint at 80 weeks}\} \times 100\%. \quad (3)$$

The PE parameter in (3) will be estimated using a Cox proportional hazards model with the indicator of assignment to a mAb group versus the control group as the sole covariate. The score test will be used to evaluate whether hazard ratio PE differs from zero. This analysis uses the same failure time as used for the primary analysis of the cumulative-incidence based PE. Goodness-of-fit diagnostics including the complementary log-log endpoint-free survival curves and the Grambsch and Therneau (1994) test will be applied to assess veracity of the proportional hazards assumption.

This Cox model analysis will be repeated, conducted as an as-treated analysis of the per-protocol (PP) cohort. This analysis is done using the same Cox model except that participants are right-censored by the event of no longer qualifying for membership in the PP cohort.

An additional secondary analysis of PE based on the Cox proportional hazards model will be done that uses as the failure time variable the time from the most recent infusion to the estimated date of HIV-1 infection. This analysis is conducted in the MITT cohort. This analysis can have increased power to detect prevention efficacy compared to the primary analysis of the cumulative incidence based parameter PE, if instantaneous prevention efficacy is higher when VRC01 concentrations are higher. Goodness-of-fit diagnostics will be applied as described above.

The Cox models are selected for the secondary analysis instead of the primary analysis in order that the validity and interpretation of the primary analysis does not depend on the proportional hazards assumption.

The Cox model may also be used for a secondary analysis to assess PE in the MITT cohort by modeling full cumulative infusion adherence (i.e., at study time  $t$ , all infusions up to and including time  $t$  received within target visit windows) or lack thereof as a binary time-varying covariate. In addition, to study the dose-response in the association of infusion adherence with PE, we will assess PE in subgroups defined by the level of cumulative infusion adherence over time, with adherence levels defined, at time  $t$ , as missing zero infusions by time  $t$ , missing at most 1 infusion by time  $t$ , missing at most 2 infusions by time  $t$ , etc., included in the model as binary time-varying covariates. If there is a time-varying covariate prognostic for subsequent HIV-1 infection that also predicts the probability of subsequently taking infusions, and taking infusions predicts subsequent values of this prognostic factor, then the Cox model described above provides biased inference (Hernán et al., 2000). Based on this, diagnostics will be done to check if there are any measured time-varying covariates strongly associated with both infection and taking subsequent infusions. If such covariates are identified, then the standard Cox model analysis described above will be supplemented with a causal structural nested Cox model analysis, which is designed to correct for time-varying confounding.

Sensitivity analyses of the primary analysis will test  $H_0 : PE = 0\%$  with a log-rank test and with a Gehan-Wilcoxon test stratified by VRC01 dose group.

To further explore potential time-variations in PE from Week 0 through to Week 80, in-

stantaneous PE over time, defined as one minus the instantaneous hazard ratio (pooled VRC01/control) over time, will be estimated using the nonparametric kernel estimation method with optimal bandwidth selection for the instantaneous hazard ratio as described in Andersen et al. (1993), with an asymptotic pointwise 95% CI. The simultaneous 95% confidence interval for instantaneous PE will be calculated following the method of Gilbert et al. (2002).

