Table 4-4 reports power calculations for comparing HIV-1 incidence between the 10 mg/kg and 30 mg/kg mAb groups. The calculations assume the scenarios for true values of PE10 and PE30 indicated in the first two columns of the table. The results show that the study is well-powered to detect large differences, for example, with about 87% power to discriminate 30% vs. 80% PE and 40% vs. 85% PE, but may miss moderate differences (e.g., 34% power to discriminate 30% vs. 60% PE). In contrast, the study has high power to correctly select the best mAb dose group given moderate efficacy differences. Specifically, if the true PE30 is moderately greater than the true PE10, then there is high probability that the estimated PE30 would be greater than the estimated PE10, such that the 30 mg/kg mAb dose group would be selected.

		Power to Rank-and-Select	Power to Detect PE10
PE10	PE30	Best mAb Dose Group ^s	Different from PE30 [#]
20%	60%	88.3	58.3
30%	60%	86.7	39.5
40%	60%	81.7	21.6
20%	70%	97.2	83.7
30%	70%	96.8	69.4
30%	80%	99.8	91.5
40%	85%	>99.9	90.8
50%	85%	99.7	77.0

Table 4-4 Statistical power for comparing the 10 versus 30 mg/kg mAb groups: Power to correctly rank-and-select the best mAb group and power to detect superiority of the 30 mg/kg mAb group over the 10 mg/kg mAb group in a head-to-head comparison

⁵ Probability that the mAb dose group that is truly better (the 30 mg/kg dose group in the scenarios considered in the table) is correctly selected based on the point estimate for PE30 exceeding that for PE10. Specifically, correct selection entails that the estimated PE30 is greater than the estimated PE10 and PE30 is significantly > 0% (1-sided α = 0.025)

[#] Cumulative hazard-based 2-sided Wald tests comparing HIV-1 incidence between the 10 mg/kg and 30 mg/kg mAb groups. Rejection of the null hypothesis requires that PE30 is significantly > 0% (1-sided α = 0.025)

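### SAP 8.2: the rejection rule for dose-response test (i) demands both inequalities although its alternative needs only one (about 1% power at PE10 = PE30 = 60%), and test (ii) has about 9% type I error

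*SAP*

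**What the plan says.** SAP 8.2 lists three further secondary tests after those of PE10 and PE30. The first is introduced as "Assess a dose-response effect by testing the null hypothesis" of equal cumulative incidence in the three arms, against 0% ≤ PE10 ≤ PE30 with one or more of the inequalities strict. Protocol 4.3 gives the same alternative.

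All three "will be tested using cumulative hazard function based Wald tests". W(i,j) is the difference in log Nelson-Aalen cumulative hazard between arms i and j at 80 weeks, divided by its standard error. The rules are:

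- **Test (i).** The SAP restates the alternative in terms of cumulative hazards, "with at least one strict inequality, and therefore the test of (i) will reject" only if W(c,10) and W(10,30) both reach the 0.975 normal quantile, 1.96.
- **Test (ii).** "The test of (ii) will reject" the same null if either |W(c,10)| or |W(10,30)| reaches 1.96. No overall level is given.
- **Test (iii).** It rejects if W(10,30) reaches 1.96.

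PE10 and PE30 are each compared with control by two-sided 0.05 "level Wald tests described in Section 8.1", which in SAP 8.1 means a "level Wald test of the equality of log cumulative hazard functions at 80 weeks for the pooled mAb group" against control. W(c,10) is therefore in effect the PE10 test statistic.

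**The concern.** The rule in (i) does not follow from its alternative. An alternative that needs one strict inequality is paired with a rule that needs evidence for both. Two cases inside the stated alternative are PE10 = PE30 = 60%, which is the design alternative, and PE10 = 0% with PE30 = 60%. In each, one of the two statistics has mean zero.

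Rule (i) rejects exactly when the unadjusted PE10 test shows benefit and test (iii) also rejects, so it adds nothing to those two results. Protocol 4.4 justifies the three-arm design largely by what it can show about dose. A pre-specified dose-response test that almost never rejects invites a misleading reading of no dose-response.

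Test (ii) does address its stated null. Its fault is the level: two chances to reject at 1.96 with no adjustment.

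**Working it through.** **Inputs.** 900 per arm (Protocol 4.6.2). Control incidence 3% per year, dropout 10% per year and follow-up 80 weeks (Protocol 4.6.1). Design alternative PE10 = PE30 = 60%, with 37 control and 30 pooled mAb events (Protocol 4.6.4), hence 15 per mAb arm.

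**1. Reproduce the plan's own figures.**

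- Expected events per arm = n·λ/(λ+d)·(1 − exp(−(λ+d)·80/52)). Control: 900 × 0.03/0.13 × (1 − e^−0.2) = 37.6. Each mAb arm at 60%: λ = 0.012, giving 15.3, or 30.5 pooled. The protocol has 37 and 30.
- Primary power, with var(log Λ) ≈ 1/events: |ln 0.4| / √(1/37 + 1/30) = 0.916/0.2457 = 3.73; Φ(3.73 − 1.96) = 96.2%. Protocol Table 4-1 gives 96.0%.
- A Nelson-Aalen simulation (exponential infection and dropout, 20,000 trials per scenario) was checked against Protocol Table 4-4, using that table's own rule ("Cumulative hazard-based 2-sided Wald tests comparing HIV-1 incidence between the 10 mg/kg and 30 mg/kg mAb groups", with PE30 also significant). At 30/60 it gives 39.7% against 39.5%, at 30/80 91.3% against 91.5%, and at 40/85 91.1% against 90.8%.

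**2. Rule (i), normal approximation.** The correlation of W(c,10) and W(10,30) is −v10/√((vc+v10)(v10+v30)), where v = 1/events.

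- At (60, 60) with 37/15/15 events: mean W(c,10) = 0.916/√(1/37 + 1/15) = 2.99, mean W(10,30) = 0, correlation −0.60. P(both ≥ 1.96) = 0.8%.
- At (0, 60) with 37.6/37.6/15.3 events: means 0 and 3.02, correlation −0.38. P(both ≥ 1.96) = 1.4%.
- Under the null: correlation −0.5, size about 0.000005.

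In the first two cases the ceiling is 2.5% whatever the number of events, because one statistic has mean zero.

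**3. Rule (i) against a trend test, simulated.** The comparator is a one-sided 0.025 contrast Σ c_k log Λ_k with c_k = (s_k − s̄)/v_k, where s̄ is the inverse-variance-weighted mean of the scores s_k. Hand check at (60, 60), scores 0, 1, 2: s̄ = 45/67 = 0.672; c = −24.85, 4.93, 19.93; mean/SE = 24.85 × 0.916/√44.8 = 3.40; power Φ(3.40 − 1.96), about 92.5%.

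| True (PE10, PE30), % | Rule (i) | Trend 0,1,2 | Trend 0,1,3 |
|---|---|---|---|
| (0, 0), size | 0.0005% (analytic) | 2.4% | 2.3% |
| (60, 60) | 1.2% | 91.7% | 87.0% |
| (0, 60) | 1.2% | 73.7% | 90.1% |
| (30, 60) | 5.0% | 86.7% | 88.7% |
| (30, 80) | 22.6% | 97.6% | 99.7% |
| (40, 85) | 40.9% | 98.9% | 99.9% |

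Trials with an arm of zero events were dropped (at most 61 of 20,000, at (40, 85)). When the ordering is reversed the trend test also rejects: 36.8% at (60, 30) and 58.0% at (60, 40) with scores 0,1,2; 24.6% and 44.9% with scores 0,1,3.

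**4. Rule (ii).** Under the null, with correlation −0.5, P(either |W| ≥ 1.96) = 0.05 + 0.05 − 0.0093 = 9.07%. The critical value that gives 5% is 2.212.

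| | Rule (ii), 1.96 | 2-df Wald | Two contrasts, 2.21 |
|---|---|---|---|
| Size | 9.1% (9.0% simulated) | 4.7% simulated | 5.0% analytic |
| Power (60, 60) | 89% | 92% | 83% |
| Power (0, 60) | 90% | 90% | 83% |
| Power (30, 60) | 64% | 81% | 49% |
| Power (60, 30) | 90% | 81% | 84% |

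**The case against.** - **Equal efficacy at both doses is arguably not dose-response.** Non-rejection at (60, 60) could be defended, since efficacy there is already tested by the primary analysis with 96.0% power. But the stated alternative includes that case, and (0, 60), a plain dose effect, gives the same 1.2%.
- **Dose is covered elsewhere.** The PE10 and PE30 tests, test (iii) and the separate correlates analyses all bear on it, so a non-significant (i) need not be read alone. This stands, and it limits the harm.
- **Rule (i) errs conservatively.** True. The cost is an uninformative test, not a false claim.
- **The figures are for one trial.** SAP 8 also pools the two AMP trials. With the SAP 9.4.1 rates and the SAP 8.1 weights, a normal approximation puts pooled rule (i) at about 35%, 55% and 81% for (30, 60), (30, 80) and (40, 85). The 2.5% ceiling when only one inequality is strict is unchanged.
- **The trend test is no free gain.** With scores 0,1,2 and no variance weighting it reduces to control versus 30 mg/kg, the existing PE30 comparison (85% at (60, 60)). At (0, 60) the weighted 0,1,2 version (73.7%) is below test (iii) alone (about 85% by normal approximation). It can also reject under reversed ordering. All true, so the weighting and scores must be fixed in advance.
- **No level is stated for (ii), and most null trials stop early.** Protocol Table 4-2 has 92.7% stopping for non-efficacy and 4.9% for harm at PE = 0%. The 9% is therefore the size of the rule on full follow-up data, and the 5% target is inferred from the other secondary tests and the 0.975 quantile.

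**Conclusion.** The concern holds. Rule (i) contradicts its own alternative in both documents, and its power is at most about 2.5% wherever only one inequality is strict (1.2% in the two cases simulated). It stays low, at 5.0% for (30, 60) and 22.6% for (30, 80), when both are strict. Rule (ii) has about 9% type I error if 5% is intended.

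The power figures assume one trial of 900 per arm, the protocol's incidence and dropout, full 80-week follow-up and no interim stopping. At PE = 60% only 4.0% of trials stop for non-efficacy (Protocol Table 4-2), so that omission matters little there. The 2.5% ceiling needs none of the event-count assumptions. These are secondary tests and no primary conclusion depends on them. The point should be fixed, but it does not threaten the trial.

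**What to change.** Amend SAP 8.2 before unblinding.

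- **Test (i), either:** replace the rule with one one-sided 0.025 ordered-alternative Wald test on the three log cumulative-hazard estimates, for example the inverse-variance-weighted trend contrast with scores fixed in advance. Say that it assumes the ordering, that it can reject when the ordering is reversed (about 37% at (60, 30) with scores 0,1,2), and that it is to be read with the PE10 and PE30 estimates and test (iii).
- **Test (i), or:** if a strict ordering of all three arms is what is meant, keep the rule, restate the alternative as 0% < PE10 < PE30, and acknowledge the low power.
- **Test (ii):** state the overall level. Then use a 2-df Wald chi-square test (critical value 5.99 at 5%), or keep the two contrasts at about 2.21 and accept 49% rather than 81% power at (30, 60).
- **Test (iii):** no change.

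The cost is SAP wording only: the estimates and variances are already computed, and no participants or data are added. The trade-offs are that a trend test is not specific to the stated ordering, and that correcting the level of (ii) gives up some power in cases such as (60, 30), from 90% to 81–84%.
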